## **4 STYDT EBROLLMENT AND WITHDRAW**

### **4.1 Inclusion Criteria**

Patient scheduled lung nodule resection by VATS is assessed for eligibility.

The inclusion criteria are as follows.

- (1) The long-axis diameter of the target lung nodule is less than or equal to 20 mm;
- (2) The inner edge of the target nodule is at least 2 cm away from major pulmonary arteries or veins to allow secure nodule excision;
- (3) patient's surgeon in charge must confirm the necessity of preoperative lung nodule localization.
- (4) Male or female  $\geq 18$  years of age

### **4.2 Exclusion criteria**

- (1) There are more than two lung nodules which are needed to be localized for simultaneous resection.
- (2) The target nodule is located in the scapula region; and percutaneous localizer is impeded by the scapula bone. Therefore transthoracic percutaneous lung nodule localization is not suitable for this subset of patients.

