## **PROTOCOL SUMMARY**

**Title:** Application of 3D printing technique in small pulmonary nodule localization: A Prospective, Randomized, Controlled, Non-inferiority Trial.

**Objective:** To evaluate the accuracy and safety of template-guided lung nodule localization compared to standard computed tomography (CT)-guided localization.

**Participants:** Surgical candidates with solitary pulmonary nodule <2 cm will be approached prior to scheduled lung resection. The necessity of preoperative nodule localization would also be evaluated by the patient's operating surgeon in charge. After acquiring patients' consent to participate into the study, enrolled patients will be randomized into the CT- or template-guided group using a previously generated random table. According to priori study, each group would have a sample size of 100 participants.

[figure not shown]
**Number of site:** This is a single-center trial and all participants would be recruited in Shanghai Pulmonary Hospital.

**Description of Intervention:** The three-dimensional printed, navigational template was created to guide percutaneous lung nodule localization. Its utility has been tested in previous feasibility trial.

**Estimated Study Duration:** From 01-10-2016 to 01-07-2019.

**Estimated Time to Complete Enrollment:** From 01-10-2016 to 01-06-2019.

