### **2.2 Study Outcome**

#### **2.2.1 Primary outcome**

The primary outcome of this study is the precision of the lung nodule localization, which was specified by the localizer deviation. As the center of the nodule is the designed target, localizer deviation is measured between the center of nodule and the localizer. Regarding to measurement of the localizer deviation, because the localizer and the target nodule might be not on the same section of the CT scan, it is impossible to accurately measure the deviation from two-dimensional images.

Therefor we reconstruct the CT images upon nodule localization into three-dimensional virtual model, and precisely measure the localizer deviation in three dimensions.

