#### **3.1 Study population and groups**

The randomized, controlled trial was approved by the institutional review board of Shanghai Pulmonary Hospital. Surgical candidates with solitary pulmonary nodule less than 2cm were prospectively recruited prior to scheduled lung resection. The necessity of preoperative nodule localization was also evaluated by patient's operating surgeon in charge. After acquiring patients' consent to participate into the study, patients were randomized into CT-guided group and template-guided group respectively.

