### **4.3 Treatment Assignment Procedures**

In order to randomly assign the participants to the two groups, a randomization list with 200 numbers was created using blocked randomization with a block size of 10. The 200 random numbers are each placed in sealed envelopes which are marked with sequential number at the cover.

Patients with scheduled lung resection are evaluated by research assistants. If the above criteria are met and patient's consent to participation has also been acquired, then the patient's information is sent to a person who is not involved with the trial by calling. Then, the accorded envelop is opened to assign the patient to template- or CT-guided localization group.

Because of the intrinsic property of the trial, no masking procedure is performed. After assignment, if the patient is allocated to template-guided lung nodule localization, research assistant needs to download the patients CT data from Picture Archiving and Communication Systems. The planned localization route is marked on CT images by patient's surgeon, then the CT data is emailed to designers for template design and printing. Because it takes about 6-8 hours for template production, all enrolled patents have to give consent to participate at least one day before the scheduled surgery.

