## **6.1 Measurement of Localization Accuracy**

The accuracy of nodule localization was defined by the deviation between the localizer and the center of the target nodule on CT images. Because the target nodule and localizer are in the three-dimensional space of a patient's thoracic cage, which may not be seen on the same cut of CT scan, it is difficult to precisely measure the deviation directly on the 2D images of CT scan. In order to accurately measure the deviation, computer-aided design (CAD) software is introduced to precisely measure the deviation.

Firstly, patient's thorax is reconstructed based on CT images upon nodule localization. Then the deviation is mathematically calculated using the CAD software.

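### The eligibility lists admit patients with two nodules to localize, although the stated population is solitary nodules, and no rule says which nodule gives the primary value

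*Combined protocol and SAP*

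**What the plan says.** The population is described twice as patients with one nodule. The Protocol Summary has "Surgical candidates with solitary pulmonary nodule <2 cm will be approached prior to scheduled lung resection", and section 3.1 has "Surgical candidates with solitary pulmonary nodule less than 2cm were prospectively recruited".

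The numbered criteria are looser. The only exclusion in section 4.2 that concerns the number of nodules is "There are more than two lung nodules which are needed to be localized for simultaneous resection". None of the four inclusion criteria in section 4.1 limits the number; the one on size reads "The long-axis diameter of the target lung nodule is less than or equal to 20 mm". Section 4.3 passes the patient on for allocation under the condition "If the above criteria are met and patient's consent to participation has also been acquired".

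For the primary outcome, section 2.2.1 states that "localizer deviation is measured between the center of nodule and the localizer", and section 6.1 defines accuracy as the "deviation between the localizer and the center of the target nodule on CT images". Section 6.2 takes procedural length as the interval from first to last scan. Section 6.3 takes the DLP shown on the scanner after the session as the patient's total exposure. Section 3.5 compares the arms by t test or Mann-Whitney test, with analysis sets made up of participants. Section 4.3 says that there is no masking.

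**The concern.** A patient with exactly two nodules to localize lies outside the stated population but meets every numbered criterion. The research assistants who screen patients apply those criteria, so the word *solitary* in the descriptive text does not reliably keep such a patient out.

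Once enrolled, this patient has two localizer deviations, while the primary outcome is written for one. The plan does not say whether to use an index nodule, the mean, the worse value or both. In an unmasked trial, a choice left open until after the procedure could be made with knowledge of the arm and perhaps of the result. The session-based time and DLP would also describe a different procedure from the one the trial sets out to compare. What is at stake is a clear population and one predefined primary value per patient.

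**Working it through.** **Eligibility, side by side**

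| Nodules needing localization | Protocol Summary and 3.1 (solitary) | 4.1 and 4.2 (lists that trigger randomization) |
|---|---|---|
| 1 | in | in |
| 2 | out | in |
| 3 or more | out | out |

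The sources disagree only in the middle row. If *solitary* were binding, a threshold of more than two would serve no purpose. One of the texts has to change on either reading.

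**Size.** The plan gives no figure on this point to reproduce. The sample size in section 3.2 does not bear on it. The inputs below are assumptions, not taken from the documents: a share f of two-nodule patients of 2–20%, a within-patient correlation ρ of 0.3–0.8, and a two-nodule session costing k = 1.5–2 times a single-nodule session in time or DLP.

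*(a) Both deviations entered as independent observations.* Design effect DE = 1 + ρ × 2f/(1 + f). Actual one-sided error = P(Z > 1.645/√DE), and actual two-sided error = 2 × P(Z > 1.960/√DE). Both are shown because section 3.2 uses one-sided 0.05 and section 3.5 two-sided 0.05.

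- f = 10%, ρ = 0.5: DE = 1 + 0.5 × 0.2/1.1 = 1.091 and √DE = 1.044. The errors are 5.8% one-sided and 6.1% two-sided.
- f = 20%, ρ = 0.5: DE = 1 + 0.5 × 0.4/1.2 = 1.167 and √DE = 1.080. The errors are 6.4% one-sided and 7.0% two-sided.
- Whole range: DE 1.01–1.27, one-sided error 5.1–7.2%, two-sided error 5.1–8.2%.

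*(b) The worse of the two deviations used.* For normal deviations the arm mean shifts by f × √((1 − ρ)/π) SD. With f of 5–20% and ρ of 0–0.5 this is 0.02–0.11 SD. A rule applied alike in both arms largely cancels; a selection made in one arm only would not. No value in mm can be given, because section 3.2 states no SD.

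*(c) Time and DLP.* The arm mean is multiplied by 1 + f(k − 1), which gives 1.01 (f = 2%, k = 1.5) to 1.20 (f = 20%, k = 2). With the same k in both arms, the expected difference between arms from this source is zero. Chance imbalance with 100 per arm has SD √(2f(1 − f)/100) in the difference of shares:

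- f = 10%: √0.0018 = 0.042. Multiplied by (k − 1), this is about 2–4% of the single-nodule mean.
- f = 20%: √0.0032 = 0.057, so about 3–6%.

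A systematic shift would need a different k in each arm.

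**The case against.** A reader might infer three stronger things from this contradiction. The documents do not support them.

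- **The type I error is inflated.** The figures in (a) require a nodule-level analysis. Section 3.5 analyses participants and section 3.2 sizes the trial in patients; nothing says that nodules are the unit. The calculation is correct for that scenario, but the plan does not describe the scenario.
- **Time and dose are inflated, perhaps doubled, and the comparison is biased.** No multiplier is given. Section 5.2 describes one scan before insertion in the template arm and one after deployment, and these might serve both nodules. The number of nodules is fixed before randomization, so an uneven split would be chance and mostly noise.
- **The nodule can be picked freely afterwards.** The criteria in 4.1 and 4.2(2) are assessed on a single target nodule, and the envelope is opened only after they are met, so a target should exist before allocation. This is a partial safeguard. It does not cover the patient in whom both nodules qualify, and no section requires the target to be recorded as the one that counts.

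It can also be argued that 4.2(1) is a slip for two or more, and that only solitary-nodule patients are ever approached. That is possible, but the text cannot settle it, and as printed the criterion admits two-nodule patients. The objection limits the consequences; the inconsistency and the missing rule remain.

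**Conclusion.** The point holds as an inconsistency in eligibility with a gap in the outcome definition. The criteria that trigger randomization admit two-nodule patients whom the population description leaves out, and for them the plan does not fix which deviation is the primary value when both nodules qualify as targets. Time and DLP may then cover two localizations.

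The size cannot be established from the documents. It is zero if no such patient is enrolled. For time and dose it is mainly added noise if the extra cost of a second nodule is similar in the two arms. The error rates of 5.1–8.2% apply only if both deviations are analysed as independent and only under the assumed shares and correlations, so they are not an estimate of this trial's error rate. The reason to act is that the population and the primary value should be unambiguous before allocation in an unmasked trial, and that the correction is nearly free.

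**What to change.** Reconcile section 4.2(1) with the Protocol Summary and section 3.1 in one of two ways.

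1. **Keep the solitary-nodule population.** Change 4.2(1) to exclude patients with more than one nodule needing localization. The cost is one word and possibly slightly fewer eligible patients.
2. **If two-nodule patients are intended,** correct *solitary* in the Protocol Summary and section 3.1. Record one index nodule per patient before the envelope is opened, and state in sections 2.2.1 and 6.1 that only its deviation enters the primary analysis. Repeat the time and DLP comparisons without two-nodule patients as a sensitivity analysis. The cost is a few sentences, one extra entry at screening and one added analysis.

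Neither option needs new visits or a new sample size.

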### **4.3 Treatment Assignment Procedures**

In order to randomly assign the participants to the two groups, a randomization list with 200 numbers was created using blocked randomization with a block size of 10. The 200 random numbers are each placed in sealed envelopes which are marked with sequential number at the cover.

Patients with scheduled lung resection are evaluated by research assistants. If the above criteria are met and patient's consent to participation has also been acquired, then the patient's information is sent to a person who is not involved with the trial by calling. Then, the accorded envelop is opened to assign the patient to template- or CT-guided localization group.

Because of the intrinsic property of the trial, no masking procedure is performed. After assignment, if the patient is allocated to template-guided lung nodule localization, research assistant needs to download the patients CT data from Picture Archiving and Communication Systems. The planned localization route is marked on CT images by patient's surgeon, then the CT data is emailed to designers for template design and printing. Because it takes about 6-8 hours for template production, all enrolled patents have to give consent to participate at least one day before the scheduled surgery.

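### One fixed, disclosed block size of 10 in an unmasked single-centre trial makes one in six allocations certain in advance for anyone who keeps a full tally

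*Combined protocol and SAP*

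**What the plan says.** Section 4.3 (Treatment Assignment Procedures) sets out the allocation: "a randomization list with 200 numbers was created using blocked randomization with a block size of 10". On the envelopes it says: "The 200 random numbers are each placed in sealed envelopes which are marked with sequential number at the cover". After eligibility and consent, the patient's details are phoned to someone outside the trial, and the matching envelope is opened. On masking: "Because of the intrinsic property of the trial, no masking procedure is performed".

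The Protocol Summary adds "This is a single-center trial and all participants would be recruited in Shanghai Pulmonary Hospital" and "each group would have a sample size of 100 participants". No section describes stratification, varying block sizes, or keeping the block size from the people who recruit.

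On who controls entry, section 4.3 says "Patients with scheduled lung resection are evaluated by research assistants", and inclusion criterion 3 in section 4.1 says "patient's surgeon in charge must confirm the necessity of preoperative lung nodule localization". On who learns the arms, section 4.3 has a research assistant retrieve the CT data of each template patient and has that patient's surgeon mark the planned route. Section 6.4.1 requires at least two research assistants at every localization.

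**The concern.** With permuted blocks of one known size, the list becomes readable towards the end of each block. Once one arm has used its places, every remaining assignment in that block is known before the next patient is approached. The last patient of every block is always known.

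Sealed envelopes and an independent opener protect the contents of the next envelope. They do not protect against counting assignments that staff have already seen, and in an unmasked trial those assignments are visible. Section 3.4 plans about 10 patients a month, so a block fills in about a month and is easy to count.

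Entry also involves judgement, since the surgeon decides whether localization is needed. A person who knew the next arm could put forward an easier or a harder nodule, or hold one back. Such selection would enter the comparison of localizer deviation directly. Adjustment for measured nodule features could repair it only in part, because the features that drive a judgement of difficulty need not all be recorded.

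**Working it through.** **Inputs.**
- Block size 10, list of 200, no masking: section 4.3.
- 100 per group: Protocol Summary. Five per arm within each block is inferred from this; it is not stated.
- Non-inferiority margin 5 mm: section 3.2.
- Difference in deviation between easy and hard nodules, D: not in the documents. Assumed to be 1, 2 or 4 mm.

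**The plan's own figure.** 200 / 10 = 20 complete blocks. 20 × 5 = 100 per arm. The list length and group sizes agree.

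**Certain allocations, full tally.** With m = 5 places per arm, the expected number of determined places per block is 2m/(m + 1) = 10/6 = 1.667. Enumerating all C(10,5) = 252 possible blocks gives 420 determined places, and 420/252 = 1.667. That is 16.7%, or 20 × 1.667 = 33.3 of 200. In simulated lists of 20 blocks, the 95% range was about 26 to 42.

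| Run of determined places at the end of the block | Blocks of 252 | Share |
|---|---|---|
| at least 1 | 252 | 100% |
| at least 2 | 112 | 44% |
| at least 3 | 42 | 17% |

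**Certain allocations, partial tally.** For an observer who sees each earlier allocation only with a given probability (simulation):

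| Earlier allocations known | Share certain |
|---|---|
| 100% | 16.7% |
| 90% | 9.8% |
| 75% | 3.9% |
| 50% | 0.5% |

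**Guessing.** Always choosing the arm with fewer patients so far is right 6.53 times in 10 (65.3%), against 50% by chance.

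**Ceiling on bias from the certain slots.** Suppose that every certain template slot received one type of nodule and every certain CT slot the other. The arms would then differ by D in those slots and by nothing elsewhere. Certain slots are on average one sixth of each arm, so bias = D/6.

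| Assumed D | Bias | Share of 5 mm margin |
|---|---|---|
| 1 mm | 0.17 mm | 3% |
| 2 mm | 0.33 mm | 7% |
| 4 mm | 0.67 mm | 13% |

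**Effect of mixed blocks.** I simulated 200-patient lists with sizes drawn at random from 6, 8, 10 and 12. The observer knows these four possible sizes and every earlier allocation, but not where each block ends. Certain allocations fall to about 0.9%, or about 2 of 200. Best-guess success is about 65.6%, essentially unchanged.

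**The case against.** **The safeguard is sound as far as it goes.** Assignment follows eligibility and consent, and an uninvolved person opens the envelope. A fixed block of 10 is also less predictable than a smaller fixed block: the certain share would be 33% at size 4, 25% at 6 and 20% at 8. This stands. The weakness is one fixed size, disclosed in an open trial, and not the number 10.

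**Surgeons are not shown to hold the tally.** A reader might infer that one in six allocations is certain for surgeons too. The documents show a surgeon acting only on that surgeon's own template patients. Unless allocations are shared, the surgeon's share is the much smaller one in the partial-tally table. This stands, and it matters because the surgeon holds the clearest discretion over entry.

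**A complete tally for the assistants is itself an inference.** Section 6.4.1 requires at least two assistants, not the same two each time, and section 4.6 allows withdrawal after randomization, so a tally built at procedures alone would miss some patients. This stands in part. Assistants also handle the assignments under section 4.3, so a complete tally is possible, though not documented.

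**A larger bias is tempting.** If every best guess were acted on, the formula would give (2 × 0.653 − 1) × 4 = 1.2 mm, 25% of the margin. The point should not rest on this. That guessing strategy needs only the running tally, whatever the block size, and mixed blocks leave it as successful as before.

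**The millimetre figures are ceilings.** No section relates nodule difficulty to deviation. Each figure also assumes perfect steering in one direction, with a suitable patient always available.

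**Conclusion.** The concern holds in limited form. For an observer who knows the block size and all earlier allocations, 16.7% of allocations (about 33 of 200) are certain in advance, including the last in every block. This rests on five per arm within each block. Research assistants could be such observers; surgeons could be only if allocations are shared. The expected bias from steering every certain slot is at most 0.17 to 0.67 mm over the assumed range for D, which is 3% to 13% of the margin.

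A reader might go further and infer that allocations were predicted, that entry was steered, or that the comparison is beyond repair. The documents support none of these. They contain no evidence that prediction took place, and adjustment for measured nodule features would recover part of any imbalance. The point is a cheap improvement to the allocation procedure, not a finding that the trial is biased.

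**What to change.** Regenerate the unopened part of the list with randomly mixed block sizes, for example 6, 8, 10 and 12. Let only the uninvolved person hold the sizes, and remove the block size from the protocol that recruiters use.

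**Cost.** A new list and re-stuffed envelopes, plus ethics review, because section 7.2 requires approval of any amendment before it takes effect. If recruitment stops partway through a block, a small imbalance is possible: at most 6 patients between arms from an unfinished block of 12 (all six places of one arm filled before any of the other).

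**Limit.** Best guesses would still be right about 65% of the time.

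**If all envelopes are already open.** Disclose the fixed block size in the report. Reconstruct from the list which allocations were predictable, and compare baseline nodule features by predicted allocation.

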### **3.3 Interim Analysis**

An interim-analysis is performed on the primary and secondary outcomes when 40% of patients have been randomized. The interim-analysis is performed by an independent statistician, blinded for the treatment allocation. The data monitoring committee will have unblinded access to all data and will discuss the results of the interim-analysis in a joint meeting, and report to the ethics committee. Based on the results of interim-analysis, principal investigator decides whether the trial continues or not. The trial will be ended if the localizer deviation is significantly larger in template-guided lung nodule localization than CT-guided localization, and no benefit is obtained for patients undergoing template-guided lung nodule localization. Otherwise, the trial will be continued.

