## **6. Outcome Evaluation**

The characteristics of nodule localization, including accuracy of nodule localization, procedural length, radiation exposure, and related complications are recorded on site by research assistant. Incidence of

localizer dislodgement and margin distance reported by frozen section analysis are collected during lung resection at the operative room.

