### **6.4 Complication Related to Nodule Localization**

#### **6.4.1 During lung nodule localization**

All lung nodule localizations are conducted with presence of at least two researcher assistants to ensure the obedience of procedure protocol and collect complication information onsite. The occurrence of pneumothorax and pulmonary hemorrhage is immediately evaluated on the CT scan after the deployment of localizer. Other infrequent complications such as vasovagal response and hemoptysis are also recorded.

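### The reason given for having no masking does not cover the primary outcome, a software measurement on CT images whose reader is neither named nor masked

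*Combined protocol and SAP*

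**What the plan says.** Section 4.3 gives one blanket statement and one reason: "Because of the intrinsic property of the trial, no masking procedure is performed".

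The primary outcome is defined in 2.2.1: "The primary outcome of this study is the precision of the lung nodule localization, which was specified by the localizer deviation". Section 6.1 explains how it is obtained: "Firstly, patient's thorax is reconstructed based on CT images upon nodule localization", and "Then the deviation is mathematically calculated using the CAD software". It does not say who does this, when, on which of the scans, with how many readers, or whether the files are coded.

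Section 6 opens with a list of items that begins with accuracy and ends "radiation exposure, and related complications are recorded on site by research assistant". Section 6.4.1 adds: "All lung nodule localizations are conducted with presence of at least two researcher assistants". Under 4.3, a research assistant also downloads the CT data for patients allocated to the template.

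The only masking stated anywhere is in 3.3: "The interim-analysis is performed by an independent statistician, blinded for the treatment allocation".

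**The concern.** The nature of the trial explains why the patient and the practitioner know the arm: one procedure uses a printed template and the other does not. It does not explain why the person measuring the outcome must know it. The measurement is made on images, and the images can be separated from the allocation.

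The only recorder the plan names is a research assistant, a role that is present at every procedure and so sees the arm. Finding the centre of a small nodule plausibly leaves some room for judgement; section 1.1 describes small ground-glass-dominant nodules as hard to recognise, although during VATS rather than on CT. The choice of scan is also open. Under 5.2 the template arm has a scan before insertion and another after deployment, and 6.1 does not say which one is measured.

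The claim rests on a between-arm difference in millimetres set against a 5 mm margin (3.2). An error common to both arms cancels in that difference. An error that depends on the arm does not, and recruiting more patients does not remove it.

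**Working it through.** **Inputs from section 3.2.** Margin 5 mm; expected difference 3.5 mm, direction not stated; 70 per group; 90% power; one-sided alpha 0.05; 100 per group planned. The SD of the deviation and the reader error are not given.

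**The plan's own figure.** Without an SD, 70 per group cannot be reproduced forward. It can only be solved backwards. With d the true difference assumed at design (template minus CT, positive meaning the template is worse):

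SD = (5 - d) / [(1.645 + 1.282) x sqrt(2/70)] = (5 - d) / 0.495

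- d = +3.5: 1.5 / 0.495 = 3.03 mm
- d = 0: 5 / 0.495 = 10.1 mm
- d = -3.5: 8.5 / 0.495 = 17.2 mm

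Each SD returns 70 by construction, so this is not independent confirmation of the sample size.

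**Effect of a reading shift.** Let the reading favour the template by b mm on average, relative to CT guidance. With SE = SD x sqrt(2/n), the chance of declaring non-inferiority when the true difference is exactly 5 mm is

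P = Phi(b/SE - 1.645)

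With b = 0 this is 5%. For 70 per group and an assumed b = 1 mm:

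- SD 3.03: SE 0.513; Phi(1.951 - 1.645) = 62%
- SD 10.1: SE 1.709; Phi(0.585 - 1.645) = 14.5%
- SD 17.2: SE 2.905; Phi(0.344 - 1.645) = 9.7%

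Other cases:

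| SD (mm) | b = 0.5, n = 70 | b = 1, n = 70 | b = 0.5, n = 100 | b = 1, n = 100 |
|---|---|---|---|---|
| 3.03 | 25% | 62% | 32% | 75% |
| 10.1 | 9% | 14.5% | 10% | 17% |
| 17.2 | 7% | 9.7% | 7.5% | 11% |

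The rate rises with the sample size because the SE shrinks while the shift stays the same.

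**Shift that makes a false claim as likely as not.** This is 1.645 x SE: 0.84, 2.81 and 4.78 mm at 70 per group, and 0.71, 2.35 and 4.00 mm at 100 per group, for the three SDs in order.

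**Opposite direction.** At SD 3.03 mm, a true difference of 3.5 mm and 70 per group, a 1 mm shift against the template cuts power from 90% to Phi((5 - 3.5 - 1)/0.513 - 1.645) = 25%. Masking therefore protects the new method as well as the comparison.

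**The case against.** The strongest reply is that the deviation is computed by software, so the reader has little discretion, and that no reader error is documented. Part of this stands. The plan does not describe how the nodule centre and the localizer are identified, so the room for judgement is plausible but assumed. The 1 mm shift is hypothetical, and only a part that differs by arm matters. But nothing in the plan shows the reading to be free of judgement either.

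Several stronger readings are tempting and are not supported:

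- **That the plan excludes masking altogether.** Section 3.3 blinds the interim statistician. The blanket sentence in 4.3 should be reconciled with this.
- **That template designers, or the assistants who attend, make the measurement.** No reader is named. Designers appear in 4.3 only for design and printing, and section 6 supports only that an assistant records accuracy on site.
- **That points are marked by hand on 3 mm slices.** Hand marking is not mentioned, and the 3 mm thickness in 5.1 describes the initial scan in the control arm.
- **That unmasked reading will carry the result across the margin.** At SD 10.1 or 17.2 mm it would take a shift of several millimetres to make a false claim as likely as not. Section 3.5 also lists only two-tailed tests of difference and no comparison with 5 mm, so the rates above belong to the test implied by 3.2. That mismatch is a separate issue.
- **That coding the files is enough, whoever reads them.** A designer has already worked on the CT data of template patients, and an assistant may have been in the room. Either could recognise a case.

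**Conclusion.** The point holds in a limited form. The reason in 4.3 does not reach the primary outcome, the reader is neither specified nor masked, and the one blinded role does not touch the measurement. The deciding outcome is thus left open to a bias that could be avoided at little cost. The change should be made; confidence is medium.

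The size cannot be fixed from the documents. The span from 9.7% to 62% at 70 per group (11% to 75% at 100) is an illustration. It rests on a back-solved SD, an assumed 1 mm shift that favours the template, a true difference of exactly 5 mm and a one-sided 5% test. None of the three SDs should be taken as the expected case, because 3.2 does not state the direction of its 3.5 mm.

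**What to change.** **Section 6.1.** State that the primary measurement uses the post-deployment scan in both arms, which 5.2 already provides. State that these scans are exported under a study code, cropped to the lung field and put in random order, and that they are measured without knowledge of allocation by an existing team member who neither attended that procedure nor designed that patient's template.

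**Section 4.3.** Limit the no-masking statement to the patient and the practitioner.

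**Section 6.** Adjust the on-site recording of accuracy so that it agrees with the masked reading.

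**Cost.** No new scan and no change to the sample size. There is some file handling and a short delay before the value is recorded. The team must have someone free of both roles for each patient; the documents do not show how the work is divided, so this needs checking. Masking may be imperfect, because the needle track may still hint at the arm.
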